connectivity besides the use of conventional fMRI regional activation paradigms of response to emotional stimuli. Preliminary findings (described below) from our studies support this hypothesis and provide rationale to conduct a definitive clinically relevant study.

2cii. Methods and Design:

We plan to recruit unmedicated 40 BDD, 60 HRUD, 60 LRUD as well as 40 HC subjects closely matched for age, gender and ethnicity for the study. We expect that at baseline 10% of subjects could be lost. During follow-up 15 - 20 % of HRUD and LRUD of patients may be lost before adequate data for development of (hypo)mania is collected. The number of subjects remaining will be adequate for statistical analysis proposed. For the exploratory aim, both the UD groups will be offered 24 months of antidepressant treatment with frequent mood assessments in the study. The other BDD and HC subjects will be followed up by phone for 24 months. During the 24 months all subjects will be rated on YMRS and the MSC-SADS for any periods suggestive of occurrence of hypomanic symptoms.

2c(ii)A. Human Subjects: The detailed inclusion and exclusion criteria and protection procedures are described in Human Subjects section E1a.

2c(ii)B. Recruitment and Timeline:

1. **Year 1:** Week 1 – 12: Training of study personnel and organization for initiation of study.
2. **Year 1 – Year 5:** Week 12 – Week 234: Recruitment of subjects and conduct of the study.
3. **Year 5:** Week 234 – Week 260: Continued follow-up of subjects and final data analysis and publication.

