2c(ii)E. Screening and follow-up procedures: All subjects will have a comprehensive baseline psychiatric diagnostic assessment for screening and if found eligible will be included in the study. BDD subjects will be referred to the treater of their choice after completing the baseline study. We have an extensive list of local treaters which can be provided to subjects and subjects guided how to get treatment. Using this process we are able to help subjects get access to treatment which many times they are not able to get on their own. Following the baseline scan, healthy subjects and BDD subjects will be given the option to be followed up by phone every three months for 24 months. Subjects will be monitored by phone for the emergence of sub-threshold or hypomanic/manic symptoms on diagnostic and symptom severity scales for depression and hypomania. UD subjects will be given the option to receive antidepressant treatment for 24 months and assessed after two weeks for first month, and every month up to 6 months for symptom improvement as well as for emergence of sub-threshold or hypomanic/manic symptoms on diagnostic and symptom severity scales for depression and hypomania. After 6 months subjects will be followed up with every 3 months visits. The baseline and follow-up procedures are detailed in Table 3.

Visit 1, the screening visit. Lasting approximately 3-6 hours, the screening will include a clinical psychiatric interview (DIGS: Diagnostic Interview for Genetic Studies or the KSADS: Kiddie Schedule for Affective Disorders and Schizophrenia)(Nurnberger et al 1994) specially designed to confirm Diagnostic and Statistical Manual (DSM-IV) diagnosis as well as provide a detailed assessment of the course of the illness and chronology of mood syndromes, and past medication and substance abuse history which has been extensively used in genetic studies of BD at our center. Subjects will also be

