administered the following scales: The Mini International Neuropsychiatric Interview (M.I.N.I.) and the Family Interview for Genetic Studies (FIGS), the Structured Clinical Interview for DSM-IV-TR Axis II Personality Disorders (SCID II), Columbia Suicide Severity Rating Scale (CSSRS), Beck Scale for Suicide Ideation (BSSI), the Hamilton Depression Rating Scale 17-Item (HAMD) or the Children's Depression Rating Scale (CDRS-R), the Montgomery-Asberg Depression Scale (MADRS), the Hamilton Anxiety Rating Scale (HAMA) or the Screen for Child Anxiety Related Disorders (SCARED), the Young Mania Rating Scale (YMRS), the Childhood Events and Life Events Scales, the Hypomania Syndrome checklist of schedule for Affective Disorders and Schizophrenia (HSC-SADS), and the Clinical Global Impression Scale-for Bipolar Disorder (CGI-BP). Patients will then undergo a full physical examination (including heart rate, blood pressure, height and weight) and laboratory tests that will include complete blood count, comprehensive metabolic panel, thyroid function tests, electrocardiogram (EKG) urine examination and a urine toxicology screen. S100B and genetic blood draw will be completed at this time as well. There will also be a serum pregnancy test conducted at this visit. Full medication, medical, and psychiatric histories will be taken.

Visit 2 will consist of the mood questionnaires, Columbia Suicide Severity Rating Scale (CSSRS), Beck Scale for Suicide Ideation (BSSI), Visual Analog Mood Rating Scale (VAS), recording of vital signs and weight, and the baseline fMRI scan. The visit will last approximately 4 hours with approximately 2 hours being spent in the scanner itself. There are occasional circumstances that are beyond our control in which the subject will not be able to scan on the indicated week. If this occurs we will make every effort possible to scan the subject as soon as possible. Upon completion of the scan, UD patients, if they agree, will be started on antidepressant treatment. Patients will be educated in detail about the side effects of antidepressant treatment, ways to avoid side effects, and how to contact the research team in case of uncomfortable side effects. The study doctor will adjust the antidepressant dose as needed throughout the study. Genetic blood draw will also be done during this visit.

Only UD subjects who opt for treatment (and sign the appropriate consent) will complete the following visits:

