Visit 3 will be one week following visit two and consist of mood questionnaires, Columbia Suicide Severity Rating Scale (CSSRS), Beck Scale for Suicide Ideation (BSSI), TESES (Treatment Emergent Side Effects Scale), and recording of vital signs and weight.

Visits 4 and 5 will be two weeks apart and consist of mood questionnaires, Columbia Suicide Severity Rating Scale (CSSRS), Beck Scale for Suicide Ideation (BSSI), TESES (Treatment Emergent Side Effects Scale), and recording of vital signs and weight.

Visit 6 through 10 will be one month apart and consist of mood questionnaires, Columbia Suicide Severity Rating Scale (CSSRS), Beck Scale for Suicide Ideation (BSSI), TESES (Treatment Emergent Side Effects Scale), and recording of vital signs and weight.

Visit 11 through 16 will be three months apart and consist of mood questionnaires, Columbia Suicide Severity Rating Scale (CSSRS), Beck Scale for Suicide Ideation (BSSI), TESES (Treatment Emergent Side Effects Scale), and recording of vital signs and weight.

BDD, Healthy control subjects, and UD subjects that discontinue medication treatment who opt for follow up (and sign the appropriate consent) will complete the following study procedures:

Phone assessments 1 through 8 will be three months apart and consist of mood questionnaires, and CSSRS/BSSI. These phone calls will take approximately 30 minutes. If subjects report significant mood changes they may be asked to come to the clinic for assessment. Assessment will be done with mood ratings done at V1 and V2.

Genetic Analysis:

A trained phlebotomist will collect the blood sample. Deoxyribonucleic Acid (DNA) is isolated from 10ml of blood using an organic procedure (Madisen et al.1987). The concentration and quality of DNA is determined using absorbance measurements at 260 and 280nm. The serotonin transporter (SLC6A4) proximal 5' regulatory polymorphism will be genotyped by DNA amplification following the protocol of Heils et al. (Heils et al. 1996). The primers stpr5; 5'-GGCGTTGCCGCTCTGAATTGC- 3' and stpr3; 5'-GAGGGACTGAGCTGGACAACCCAC-3' generate 484 and/or 528 base pair products. The amplification reactions are electrophoresed through 3% agarose and visualized by ethidium bromide staining using a UV transilluminator.

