2c(ii)F. Antidepressant treatment: SSRIs are the most frequently prescribed antidepressants and are generally well tolerated. We will use SSRI antidepressants or Wellbutrin which are available in generic form i.e. either sertraline, fluoxetine, paroxetine, vilazodone, citalopram, or bupropion. We have elected to use these medications because there is some evidence that they are less likely to induce (hypo)mania. Subjects treatment will be tailored according to clinical needs and the dose adjusted or the medication switched depending on response and side effects. If a patient satisfies criteria for conversion to BD (please see section 2c(ii)G below) at any time during follow-up, the study will be terminated, and either the antidepressant would be withdrawn and the patient treated with a mood stabilizer or continued and a mood stabilizer added upon. Once the patient is stabilized they will be referred to the treater of their choice or to an inpatient facility for appropriate treatment. If at any time point the patient requires other treatment e.g. due to treatment resistance or wants to be treated with psychotherapy only then they will be referred to a treater of their choice but would continue to come for follow-up visits for assessment of mood.

Patients with psychotic symptoms, who can be safely treated as an outpatient, will also be treated with an atypical neuroleptic of their choice per treatment guidelines⁵. The dosage and duration of use of these medication will be recorded, converted to a single standard equivalent and used in the data analysis as detailed in section 2c(ii)la.(adjusting for covariates).

2c(ii)G. Rating Scales:

I. Diagnostic Instruments:

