E2b7. Treatment and Referral after the study: While the BD subjects is being screened and the fMRI scan being arranged and for the UD patients when they are coming to the end of the 24 months supervised treatment, we will start the process of identifying with the patients where they would like to be referred for treatment. A range of treatment options are available in the Indianapolis area including private university and other outpatient clinics and state hospital. We already have a handout available for all the addresses and phone numbers for patient to make an appointment which we routinely give to our research subjects after they finish the study with us. In this study, we will additionally call up the treater of the patient's choice and make sure that subjects will have an appointment. UD subjects will still be followed up every 3 months until the end of the study. As the patients included in this study will present as unmedicated because either they have never been diagnosed before or for some other reason elected not to take medication that was recommended (not an uncommon situation for many young patients) this process will help in patient complying and following through with treatment. In this way we will be able to get patients engaged in treatment which otherwise they are unlikely to get on their own.

E2b8. Loss of confidentiality: Documents which contain patient-identifying data will be kept in locked filing cabinets, with access restricted to authorized investigators participating in the research, and secretarial and administrative personnel who have been informed about the requirement to maintain confidentiality. Computer records that contain patient identifying data will be secured by passwords. Patients will not be identified in any reports or publications that may result from this study. University policies regarding HIPAA regulations for research subjects will be followed.

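### The follow-up lists assign no assessments to UD subjects who decline antidepressant treatment at baseline, although the plan says all subjects will be rated for 24 months

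*Combined protocol and SAP*

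**What the plan says.** All references are to the combined protocol and SAP.

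**Treatment is optional.** In Methods and Design, "both the UD groups will be offered 24 months of antidepressant treatment with frequent mood assessments in the study". Under Visit 2 in 2c(ii)E, "UD patients, if they agree, will be started on antidepressant treatment".

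**Who is assessed afterwards (2c(ii)E).**
- Clinic Visits 3 to 16: "Only UD subjects who opt for treatment (and sign the appropriate consent) will complete the following visits".
- Phone assessments 1 to 8, three months apart: "BDD, Healthy control subjects, and UD subjects that discontinue medication treatment who opt for follow up".
- The phone option after the baseline scan: "healthy subjects and BDD subjects will be given the option to be followed up by phone every three months for 24 months". UD subjects are not named.

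**Text that points to wider follow-up.**
- Methods and Design: "During the 24 months all subjects will be rated on YMRS and the MSC-SADS".
- 2c(ii)F, on a patient who at any point needs other treatment or wants psychotherapy alone: they are referred out, "but would continue to come for follow-up visits for assessment of mood".
- E2b7, in the paragraph on referral as supervised treatment ends: "UD subjects will still be followed up every 3 months until the end of the study".
- Table 3 is titled as the follow-up schedule for UD subjects, with no split by treatment choice. The Aim 3 analysis text relies on it.

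**Text that points the other way.** E2b10 applies to patients who want a treatment that the study cannot provide the same handling as to those who become manic: they leave the study and are referred.

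**The concern.** Discontinuing a drug presupposes having started it. A UD subject who declines at baseline is therefore outside the clinic list, the phone list and the phone option. Such subjects are foreseeable. E2b7 says some recruits will be unmedicated because they chose not to take recommended medication, and calls this not unusual in young patients.

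Aim 3 asks whether baseline imaging predicts conversion to bipolar disorder and models time to conversion in UD subjects. If decliners are not assessed, they contribute no person-time and no events. The loss also depends on a treatment choice that may be related to illness. Section E1b8 states that antidepressants can precipitate mania, so the sample would be selected on an exposure that the protocol itself links to the outcome. Section E2b6 is more guarded about that risk in high-risk UD subjects, so the direction of any bias cannot be fixed from the documents. No section says how decliners are followed, censored or analysed, and the covariate list does not name antidepressant use during the study.

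**Working it through.** **Step 1: set the texts side by side for a UD subject who is scanned and declines.**

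| Source | Does it give this subject an assessment? |
|---|---|
| 2c(ii)E, Visits 3 to 16 | No: treatment takers only |
| 2c(ii)E, phone calls 1 to 8 | No: UD subjects who stop treatment only |
| 2c(ii)E, phone option after the scan | No: healthy and BDD subjects only |
| Methods and Design | Yes in principle, but with no schedule for this subject |
| 2c(ii)F | Yes if psychotherapy or another treatment is wanted; silent if none is wanted |
| E2b10 | No if the wanted treatment is unavailable in the study |
| Table 3 | Unclear: titled for UD subjects, but marks antidepressant treatment at baseline and every follow-up |
| E2b7 | Unclear: three-monthly follow-up, in the context of supervised treatment ending |

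The operational lists contradict the general statement, and 2c(ii)F and E2b10 pull in opposite directions.

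**Step 2: inputs for size.** From the sample-size section, Aim 3: 60 HRUD and 60 LRUD subjects, conversion 14% and 6%, attrition 20% in both groups. Assumed, because the documents give no figure: a decline share p of 10%, 20% or 30%, equal in both groups.

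**Step 3: the plan's own figure.** The plan states 80% power. A two-sided comparison of 6% with 14% at n per group has power Φ[(0.08 − 1.96√(0.18/n)) / √(0.1768/n)], where 0.18 = 2 × 0.10 × 0.90 and 0.1768 = 0.06 × 0.94 + 0.14 × 0.86. At n = 60 × 0.8 = 48 this gives 25.5%, so the 80% is not reproduced. That shortfall exists whether or not decliners are followed. It is a separate matter, and the figure serves here only as the baseline.

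**Step 4: expected conversions.** With everyone followed, 60 × 0.14 + 60 × 0.06 = 8.4 + 3.6 = 12. After 20% attrition, 12 × 0.8 = 9.6. If decliners are lost in addition, events = 12 × (1 − p) × 0.8.

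| p | UD subjects without follow-up (120p) | n per group | Expected events | Power, 6% v 14% |
|---|---|---|---|---|
| 0% | 0 | 48.0 | 9.6 | 25.5% |
| 10% | 12 | 43.2 | 8.6 | 23.4% |
| 20% | 24 | 38.4 | 7.7 | 21.2% |
| 30% | 36 | 33.6 | 6.7 | 19.1% |

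**Step 5: if the planned 20% already includes decliners.** At p of 10% or 20% nothing further need be lost and 9.6 stands. At 30% the decliners alone exceed the allowance, and at most 12 × 0.7 = 8.4 events remain.

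**Step 6: what the phone pathway would give.** Table 3 has seven assessments of treated UD subjects in the first six months (weeks 2 and 4, months 2 to 6). Three-monthly calls give two. After month 6 both are three-monthly.

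**The case against.** The strongest reply is that the plan already intends to follow these subjects. Methods and Design covers all subjects, Table 3 is not split by treatment choice, 2c(ii)F keeps psychotherapy-only patients in assessment from any time point (which can include baseline), and nothing removes decliners from the Cox model. This stands against the stronger reading that a reader might draw, that decliners are excluded from the conversion analysis or that Aim 3 will estimate conversion only in antidepressant takers. The documents do not say that. It would happen only if the visit lists were applied as written. The reply does not remove the contradiction, and it gives no schedule to a subject who wants no treatment at all.

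A reader might also infer that decliners are the main source of untreated conversion data. The documents do not support this. They give neither a decline rate nor a discontinuation rate, and subjects who stop treatment, as well as those on psychotherapy alone, also supply time off drug.

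The size is open to challenge too. The decline share is assumed, and Methods and Design describes its 15% to 20% loss broadly enough that it may already cover decliners. Even without overlap the loss is 1.0 to 2.9 events, in an aim labelled exploratory that is short of events in any case. All of this stands, and it limits the weight of the point. The selection on treatment choice remains, and it does not depend on the event count.

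**Conclusion.** The point holds as an internal contradiction with a foreseeable consequence. The lists in 2c(ii)E give no assessments to UD subjects who decline treatment at baseline, against the statement that all subjects are rated for 24 months, and 2c(ii)F and E2b10 need reconciling. If the lists are followed, the exploratory Aim 3 sample is selected on accepting an antidepressant. Expected conversions then fall from 9.6 to between 8.6 and 6.7, assuming 10% to 30% decline, equally in both groups and on top of 20% attrition. The fall is smaller, or nil up to 20% decline, if the planned attrition already includes decliners. The baseline comparisons of Aims 1 and 2 are not affected. It is worth correcting before follow-up starts, because assessments not made cannot be fully recovered later.

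**What to change.** - In 2c(ii)E, extend the phone-assessment list to UD subjects who decline or discontinue medication treatment. Extend the phone option after the scan and the follow-up consent to match.
- Reconcile 2c(ii)F with E2b10 on whether mood assessment continues for a patient who wants treatment that the study does not provide. This concerns data collection only; how such patients are treated is for the investigators.
- In the Aim 3 analysis text, define the risk set as all scanned UD subjects who consent to follow-up, with time zero at the baseline scan. Record antidepressant exposure, and state how decliners are censored.
- Allow for conversion times known only to the interval between two assessments, for example with an interval-censored or discrete-time hazard model.

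The cost is a few lines of text, a possible consent change, and up to eight calls of about 30 minutes per decliner: 12 × 8 = 96 calls at 10% decline, 36 × 8 = 288 at 30%. The drawback is that decliners would be assessed less often than treated UD subjects in the first six months, so the timing of conversion would be known less exactly for them. The question about periods since the last visit, asked at each follow-up, softens this but does not remove it, hence the interval-based analysis.

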All gel photographs will be examined independently by at least two technical personnel before a genotype is assigned. If there are any ambiguities, the genotyping will be repeated on a new amplification product. The technical staff will be working with DNA numbers only and will not have knowledge of the clinical status of the individuals being genotyped. Individuals with known genotypes will be used as controls, and a negative control (no DNA added) will be included with each run. All necessary precautions will be taken to avoid contamination.

Micro arrays. We will collect 10 cc of blood at screening for micro array analysis of gene expression. Micro arrays, standard technique will be used to obtain RNA and to purify the RNA (RNeasy mini kit (Qiagen, Valencia, CA) from dissected BLA tissues. The quality and quantity of total RNA will be evaluated by 260/280 ratios and by 260nm UV absorption (Beckman, DU 640B spectrophotometer (Beckman Coulter, Fullerton, CA)). We will use Murine Genome U74A and Bv2 oligonucleotide arrays (Affymetrix, Santa Clara, CA) in a procedure recommended by manufacturers. Thus, T7-linked oligo (dT) primer will be used to reverse transcribe the mRNA, and biotin-labeled cDNA will be generated using the Enzo Bio Array High Yield RNA Transcript Labeling Kit (Enzo Diagnostics, Farmingdale NY). Samples will be hybridized at 45°C for 16 hours under constant rotation. Arrays will be washed and stained using the Affymetrix Fluidics Station 400 and will be scanned using Affymetrix GeneArray Scanner 2500 following manufacturer's recommendation.

Gene identification. The Affymetrix Interactive Query feature will be used to identify each gene name from the probe-set information. In the case where the Affymetrix website did not identify a known gene by name, a National Center for Biotechnology Information Blast analysis will be carried out to identify the closest known gene existing in the database.

S100B, Antibody, and Cytokines Analysis

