A trained phlebotomist will also collect an additional 3.5 mL to 5.0 mL of blood at screening for S100B and cytokines analysis. The BD Vacutainer Tube will contain a clot activation chemical and inert silica gel to facilitate with the separation of the plasma from the whole blood. Blood will be allowed to clot for 20-30 minutes at room temperature and centrifuged at 2000 rpm for 10 minutes. The blood will then be processed and serum/plasma will be collected within 2-4 hours. The serum samples will be stored at 2-8°C for 24 hours. For longer storage samples will be frozen to below -80°C. Samples are stable for 6 months at -20°C. Frozen serum must be gently, but thoroughly mixed after thawing. Repeated freeze-thaw cycles will be avoided.

Samples which are grossly lipemic or contaminated will not be used. Samples containing precipitates will be centrifuged before testing. Heat-inactivated samples will not be used as well.

Samples will be stored in [name] laboratory in the Lerner Research Institute until they are analyzed. All samples will be de-identified and assigned an internal number. Serum samples will then be stored at -80°C to be analyzed in batches. Serum's ID will be matched to consent forms and research record. S100B measurements will be performed using Elisa kits (98 wells, anti-human S100B, Diasorin) and reading will be done using a multi-plate fluorescent reader. Fluorescent signals were converted into ng/ml as per standard curve concentrations.

Antibodies to S100B have recently been measured and described as an indicator of remote and chronic elevation of S100B. The presence of the antibodies could also signify development of brain inflammation against astrocytes. Therefore, we will also measure S100B antibodies using previously described methods. Blood will also be collected for future analysis of other cytokines such as interleukins and TNF-alpha as elevated levels of these cytokines have also been implicated in the pathogenesis of mood disorders.

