3. HUMAN SUBJECTS

E1a. Human Subjects Characteristics:

The human subjects age range 16 - 30 yrs (inclusive) involved in this study will be - 40 BDD, 60 HRUD, 60 LRUD and 40 healthy control subjects matched as a group for age, gender and ethnicity who will be studied at baseline. BDD and UD subjects will be matched for depression severity at the time of the scan. However, it is likely that, by definition the BDD and UD subjects will be different in terms of other illness characteristics such as duration of illness, number of episodes, and history of alcohol and substance abuse. We will treat those illness variables as covariates in our statistical analysis (as described in section 2c(ii)1a above) to take into account the potential confounding effects of some of these variables.

Inclusion criteria for BDD patients:

1. Ages 15 - 30 years (inclusive) and able to give voluntary informed consent (consent will be taken from both parents and child for children under the age of 18)
2. Satisfy criteria for Diagnostic and Statistical Manual 4th edition (DSM-IV-TR) for Bipolar I or II disorder
3. Satisfy criteria for DSM-IV depressive episode-current
4. 17-item Hamilton Depression Rating Scale > 15 but < 25;
5. Young Mania Rating Scale score < 10
6. Satisfy criteria to undergo an MRI scan based on MRI screening questionnaire.
7. Able to be managed as outpatients during the study as ascertained by the following –
 - i. Clinical Global Severity Scale < 5 i.e. moderately ill;
 - ii. No significant suicidal or homicidal ideation or grossly disabled.

Inclusion criteria for All UD patients:

1. Ages 15 - 30 years and able to give voluntary informed consent (consent will be taken from both parents and child for children under the age of 18).
2. Satisfy criteria for DSM-IV-TR Major Depressive Episode using a Structured Interview
3. Never met criteria for mania or hypomania
4. 17-item Hamilton Depression Rating Scale score (HDRS) > 15 and < 25.
5. Young Mania Rating Scale (YMRS) score < 10
6. Satisfy safety criteria to undergo an MRI scan
7. Able to be managed as outpatients during the study as ascertained by the following –
 - i. Clinical Global Severity Scale < 5 i.e. moderately ill;
 - ii. No significant suicidal or homicidal ideation or grossly disabled

Additional Inclusion criteria for High Risk UD (HRUD) patients beside the inclusion criteria for UD:

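### The gene-expression assay cannot be carried out as written: human blood is collected, but the plan specifies dissected tissue and mouse arrays

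*Combined protocol and SAP*

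**What the plan says.** Section 2c(ii)E, under Genetic Analysis, sets out the expression work in one paragraph. The sample is blood: "We will collect 10 cc of blood at screening for micro array analysis of gene expression". The RNA is to be purified "from dissected BLA tissues", and the abbreviation is not defined anywhere in the protocol. The platform is given as "We will use Murine Genome U74A and Bv2 oligonucleotide arrays".

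The Gene identification paragraph that follows states: "The Affymetrix Interactive Query feature will be used to identify each gene name from the probe-set information". Where that returns no named gene, a BLAST search for the nearest known gene is the fallback.

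The subjects are described in section E1a: "The human subjects age range 16 - 30 yrs (inclusive) involved in this study will be - 40 BDD, 60 HRUD, 60 LRUD and 40 healthy control". The next assay in section 2c(ii)E, the S100B ELISA, names a reagent that fits the species: "anti-human S100B, Diasorin".

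On volume, section E2b2 puts the total drawn at screening at around 10 cc, which it equates with one tablespoon, plus two tablespoons on the scan day. Section 2c(ii)E lists 10 cc for micro arrays at screening, a further 3.5 to 5.0 mL at screening for S100B and cytokines, and 10 mL for DNA.

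**The concern.** A reader who follows the paragraph in order meets two mismatches. The sample collected is blood, but the material to be processed is dissected tissue. The subjects are human, but the arrays carry mouse probes. Either one prevents the assay from being performed on the study's samples as specified. The second also undermines any result, because probes built on mouse sequence are not a valid default for quantifying human transcripts.

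What is at stake is limited but real. Blood is taken from research participants, and eligibility starts at age 15, so minors are among them. The assay that blood is meant for is mis-specified, and no analysis of it is described. A laboratory that substituted a suitable array would be departing from the protocol without any record of the change. The stated screening volume also appears too small for the samples listed.

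**Working it through.** The plan gives no statistical figure to reproduce here. The check is a comparison of passages, plus one addition for the blood volume.

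**Sample, tissue and platform**

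- Sample collected: blood, at screening (2c(ii)E, Micro arrays).
- RNA source: dissected tissue (same paragraph). No visit description in 2c(ii)E and no row of Table 3 includes taking or dissecting tissue. These statements cannot both hold.
- Species of subjects: human, 40 + 60 + 60 + 40 = 200 planned (E1a).
- Species of array: mouse (2c(ii)E, Micro arrays). No part of the protocol describes an animal component, a human array or a rationale for cross-species hybridisation.
- Annotation: names come from the probe sets of those same arrays, with BLAST as a fallback. No mouse-to-human mapping is described, so this step does not repair the mismatch.
- Contrast: the S100B kit is specified as anti-human, so the protocol does state reagent species correctly where it describes another blood assay.

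**Where expression data are used**

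- Aims and hypotheses (section 1): not mentioned.
- Statistical analysis (2c(ii)Ia): not mentioned.
- Sample size and power (2c(ii)Ib): not mentioned.
- Table 3: no micro array row. It lists a genetic blood draw and S100B, antibody and cytokine testing.

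**Screening blood volume**

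- Stated total (E2b2): about 10 cc.
- Micro array plus S100B/cytokine samples, both placed at screening: 10 + 3.5 = 13.5 mL to 10 + 5.0 = 15.0 mL.
- Excess over the stated total: 3.5 to 5.0 mL, or 35% to 50% of 10 mL.
- If the 10 mL DNA sample is also drawn at screening, the sum is 23.5 to 25.0 mL. Its timing is unclear: Table 3 marks the genetic draw at screening only, while the visit descriptions place one at Visit 1 and another at Visit 2.
- The safety laboratory tests and the serum pregnancy test come on top, with no volume given.

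**The case against.** The strongest reply is that this is a drafting slip with no practical consequence. No laboratory could follow the sentence literally, because there is no tissue to process. Drawing blood does not commit anyone to a particular array, and the text can be corrected before anything is hybridised. The surrounding genotyping and S100B text describes assays on human samples, which suggests a local error. Nothing in the aims depends on expression data.

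Most of that stands, and it limits the point. A reader might infer that expression data from all 200 subjects will be lost. The documents do not support this: they show a mis-specified assay and do not show which array would in fact be used. Nor do they say that every subject gives the micro array sample. That is a reasonable reading of an unrestricted sentence, but no group is named and Table 3 has no row for it. Multiplying 10 cc by 200 gives about 2 litres, which measures neither bias nor the burden on any one person. Since other blood is taken at screening, the added burden may be extra volume and not an extra needle. Reading the undefined abbreviation as brain tissue, or the paragraph as carried over from an animal protocol, is plausible inference only. The contradiction needs neither.

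On volume, E2b2 says around 10 cc and equates this with a tablespoon. If a tablespoon is taken as about 15 mL (an assumption; the protocol does not say), it would just hold the two samples. It would leave nothing for the laboratory tests or any DNA sample, and it would not agree with the 10 cc beside it.

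The reply does not remove the defect. The paragraph is an operative assay specification, and nothing elsewhere in the protocol corrects it.

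**Conclusion.** The concern holds as an internal inconsistency. The expression assay cannot validly be carried out as written, because the sample, the RNA source and the array species do not agree. The tissue contradiction is shown by the protocol alone. The species conclusion rests on one general premise, that mouse-sequence probes are not a valid default for human transcripts, and the protocol offers no argument for an exception.

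The reach is one assay. A reader might infer that the trial's findings are at risk, but the imaging aims, the SLC6A4 genotyping and the S100B testing do not depend on this paragraph. It should be corrected before any micro array sample is processed, though it does not bear on the main conclusions.

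The volume discrepancy is separate and smaller: 13.5 to 15 mL from two listed samples against about 10 cc stated, and more if the DNA sample falls at screening. This assumes that the micro array and S100B samples are separate draws. The S100B text supports that by calling its sample additional.

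**What to change.** If expression analysis is intended, state that RNA comes from the blood collected, replace the tissue wording, and name a human expression platform with annotation to human genes. Add the sample to Table 3, say which groups give it, and add a short statement of how the data will be analysed, including control of multiplicity. The choice of platform is the sponsor's; the documents give no basis for preferring one.

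If no expression analysis is intended, delete the Micro arrays and Gene identification paragraphs together with the 10 cc draw.

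In the same edit, reconcile the screening volume in E2b2 with the samples listed in 2c(ii)E, including the visit at which the DNA sample is drawn, and carry the agreed figure into any participant information that repeats it.

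The cost is a text amendment with no new procedure. Deletion would reduce the volume drawn.
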